## EXECUTIVE SUMMARY

The PCORnet Bariatric Study (“the study”) team has prepared a detailed analysis plan for accomplishing the main study aims. This plan was developed by the Methods Core with feedback from the Scientific Core, Executive Bariatric Stakeholder Advisory Group, and the Clinical Data Research Network (CDRN) Bariatric Principal Investigators.

The study seeks to answer three main scientific questions:

**Aim 1:** To what extent does weight loss and weight regain differ across the three most common bariatric surgical procedures in the United States – Roux-en-Y Gastric Bypass (RYGB), Adjustable Gastric Banding (AGB), and Sleeve Gastrectomy (SG) – at 1, 3, and 5 years after surgery?

**Aim 2:** To what extent do the three most common bariatric procedures in the United States differ with respect to diabetes status at 1, 3, and 5 years after surgery?

**Aim 3:** What is the frequency of major adverse events for the three most common bariatric procedures in the United States at 1, 3, and 5 years?

**Aim 4:** To what extent do bariatric surgery outcomes explored in Aims 1-3 differ with respect to **baseline depression diagnosis** at 1, 3, and 5 years after surgery?

**Aim 5:** To what extent do bariatric surgery outcomes explored in Aims 1-3 differ with respect to **race and ethnicity** at 1, 3, and 5 years after surgery?

**Aim 6:** To what extent do bariatric surgery outcomes explored in Aims 1-3 differ with respect to **baseline age 65+ versus <65** at 1, 3, and 5 years after surgery? (**Aim 6 will only be conducted if time and resources allow this work**)

**Population:** The study will include adults, children, and adolescents less than 80 years old at time of surgery who had one of the three most common procedures in the United States (RYGB, AGB, or SG) during the years 2005 to 2015. To be eligible for the study all patients will also need to have a Body Mass Index (BMI) measurement in the year prior to surgery that is at least 35 kg/m^2.

**Data:** All data necessary for accomplishing the main scientific aims of this study will be derived from the PCORnet Common Data Model (CDM). In the plan below we have specified each CDM table that will be accessed as well as the key variables that will be examined. Although all of the tables described are necessary to complete the study, of greatest interest are the procedures, diagnosis, vitals, prescribing, dispensing, and death tables. All data for this study will be abstracted from the CDM tables at each participating health care site and then sent using secured file transfer methods to the data coordinating center at Harvard Pilgrim and to Kaiser Permanente Washington Health Research Institute for analysis.

**Analyses:** The “primary analyses” will address the main study questions outlined above using individual-level patient data. We will conduct three pair-wise comparisons for each study aim – comparing AGB versus RYGB, SG versus RYGB, and AGB vs. SG. To address potential confounding bias in each comparison, we will first use a logistic regression model to estimate the propensity score (PS), which is

defined as the probability of receiving a treatment of interest (e.g., RYGB) in each pairwise comparison given the potential confounders variables plus calendar year. We will conduct sensitivity analyses to assess for changes in outcomes by calendar year, and we will use a multiple imputation approach to address missing outcome information. Finally, for each aim, we will seek to identify heterogeneity of treatment effects, with any differences in the effects of the bariatric procedures across key subgroups (e.g., race/ethnicity).

**Methodology Standards:** Throughout the document, references are made to PCORI's Methodology Standards (e.g., [RQ-1]). A description of these standards can be found [here](#) on the PCORI website

## AIMS AND ANALYTIC PLAN SYNOPSIS

This section provides an overview of the primary and secondary analyses for each aim, as well as their primary and secondary outcomes. An overview of sensitivity analyses and analyses of heterogeneity of treatment effects is also provided for each aim.

### A. AIM 1 (WEIGHT LOSS AND WEIGHT REGAIN)

To what extent does weight loss and weight regain differ across the three bariatric surgical (RYGB, AGB, and SG) at 1, 3, and 5 years?

Primary Analysis: Complete three pairwise comparisons (RYGB vs. AGB; RYGB vs. SG; AGB vs. SG) for our primary and secondary outcomes and all sensitivity/heterogeneity analyses on adults  $\geq 20$  years of age using *individual-level data with multiple imputation for missing weight data after surgery*

Secondary Analysis: Complete three pairwise comparisons for our primary and secondary outcomes and all sensitivity/heterogeneity analyses using *distributed data analysis approach*

Primary Outcome: percentage change in weight (in kg) at 1, 3, and 5 years compared to baseline

Secondary Outcomes: 1) weight regain at 3 and 5 years; estimated as percent regain from the maximum weight (in kg) loss in the first 2 years; 2) a post-operative body weight that is  $<5\%$  lower than the pre-surgical weight at 1, 3, or 5 years after bariatric surgery; and 3) proportion achieving  $>5\%$ ,  $>10\%$ ,  $>20\%$ , and  $>30\%$  weight loss at 1, 3, and 5 years

Sensitivity Analyses (for primary outcome): 1) Calendar Year analysis: look at the effects of these procedures on weight changes by calendar year

Heterogeneity Analyses (for primary outcome): 1) Complete all analyses on adolescents  $<20$  years of age; 2) Compare comorbidity groups (e.g., baseline diabetes) or comorbidity index score quartiles 3) Compare baseline BMI ( $\geq 50$  vs  $<50$  kg/m $^2$ ), 4) Compare adults  $<65$  years and 65+ years; 5) Compare race/ethnicity (e.g., non-Hispanic black, Hispanic, non-Hispanic white), 6) Gender (male vs. female)

### B. AIM 2 (IMPROVEMENTS IN DIABETES RISK)

To what extent do these bariatric procedures differ on improvements in diabetes risk at 1, 3, and 5 years?

Primary Analysis: Complete three pairwise comparisons (RYGB vs. AGB; RYGB vs. SG; AGB vs. SG) for our primary and secondary outcomes and all sensitivity/heterogeneity analyses on adults  $\geq 20$  years of age using *individual-level data with multiple imputation for missing weight data after surgery*

Secondary Analysis: Complete three pairwise comparisons for our primary and secondary outcomes and all sensitivity/heterogeneity analyses using *distributed data analysis approach*

Primary Outcomes: 1) Rate of diabetes remission (HbA1c  $<6.5\%$  off diabetes medications  $\geq 90$  days);

Secondary Outcomes: 1) Rate of relapse of diabetes after initial remission (restart of medication or HbA1c  $\geq 6.5\%$ ), and 2) Change in HbA1c at 1, 3, and 5 years;

Sensitivity Analyses (for primary outcome): 1) Calendar Year analysis: look at the effects of these procedures on diabetes remission by calendar year

Heterogeneity Analyses (for primary outcome): 1) Complete all analyses on adolescents  $\leq 20$  years of age; 2) Compare individuals with poorly controlled diabetes (HbA1c  $\geq 7\%$ ) vs. controlled diabetes at baseline, 3) Compare insulin use vs. no insulin at baseline; 4) Compare comorbidity groups or comorbidity index score quartiles; 5) Compare baseline BMI ( $\geq 50$  vs  $<50$  kg/m $^2$ ), 6) Compare race/ethnicity (e.g., non-Hispanic black, Hispanic, non-Hispanic white), 7) Compare adults  $<65$  years and 65+ years; 8) Gender (male vs. female).

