## D. AIM 4 (SURGERY OUTCOMES AND BASELINE DEPRESSION)

To what extent do bariatric surgery outcomes explored in Aims 1-3 differ across three bariatric procedures (AGB, RYGB, and SG) with respect to baseline **depression diagnosis** at 1, 3, and 5 years after surgery?

Analyses: Complete heterogeneity in treatment effect (HTE) analyses for three pairwise comparisons (RYGB vs. AGB; RYGB vs. SG; AGB vs. SG) for primary and secondary outcomes from Aims 1-3.

Outcomes (and comparisons):

- (1) Percent total weight loss at 1, 3, and 5 years (difference in percent total weight loss)
- (2) Proportion of patients with >5%, 10%, 20%, and 30% total weight loss (odds ratio)
- (3) Rate of diabetes remission (hazards ratio)
- (4) Rate of relapse after initial remission (hazards ratio)
- (5) Change in HbA1c at 1, 3, and 5 years (difference in change in HbA1c)
- (6) Time until reoperation or reintervention with and without endoscopy (hazards ratio)
- (7) Time until all-cause mortality (hazards ratio)
- (8) Time until hospitalization (hazards ratio)
- (9) Proportion of patients with 30-day composite adverse events (odds ratio)

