### A. AIM 1 (WEIGHT LOSS AND WEIGHT REGAIN)

#### 1. Primary analysis

The primary analysis will include only patients who meet the eligibility criteria for the study and key baseline covariates (age, sex, and baseline BMI). Table 5 below shows important baseline covariates.

Continuous variables include age, baseline BMI, HbA1c, hospital length of stay during the year prior to surgery, and comorbidity score. Categorical variables include race/ethnicity, insulin use, oral hypoglycemic medication use, CDRN, node site, and year of surgery. We will aggregate comorbidity data into a score derived by combining conditions included in the Charlson and Elixhauser measures that has been externally validated among Medicare enrollees and is predictive of 30-day, 90-day, 180-day and 360-day mortality. This comorbidity score can be efficiently calculated using code from a Mini-Sentinel tool. It includes age, sex, and 37 unique health conditions including both physical and mental health comorbidities. Smoking will be operationalized as current, never, or other.

The outcome of interest will be percentage change in body weight in kilograms (from baseline) at the end of 1 year, 3 years, and 5 years after surgery [CI-3]. As it is a continuous variable, we will inspect the distribution of the variable and transform it as appropriate. We will conduct three pair-wise comparisons – AGB versus RYGB, SG versus RYGB, and AGB vs. SG. For each comparison, we will first use a logistic regression model to estimate the propensity score (PS), which is defined as the probability of receiving the treatment of interest (which can be chosen arbitrarily) in each pairwise comparison given the potential confounders listed in Table 6 plus calendar year. The PS model will be fit at each site. We

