## B. AIM 2 (IMPROVEMENTS IN DIABETES RISK)

### 1. Primary analysis

The analytic framework for Aim 2 is similar to that described in Aim 1. The primary analysis will have three pairwise comparisons. The primary outcome of interest is: (1) remission from diabetes (a time-to-event outcome), defined as HbA1c <6.5% after 90+ days of not having any active anti-hyperglycemic prescription order or dispensing post-surgery. We will estimate the PSs as described in Aim 1, and fit a Cox proportional hazards model to estimate the effects of surgery on diabetes remission, with a maximum follow-up of 1, 3, or 5 years after surgery [CI-3]. In addition to regression, matching, and weighting considered in Aim 2, PS stratification is also compatible with Cox regression. Specifically, we can fit a stratified Cox regression stratifying on site and site-specific PS percentiles (e.g., deciles). The secondary outcome of interest is the differential impact of the procedures on glycemic control, measured as change in HbA1c from baseline to 1, 3, and 5 years. As this secondary outcome is a continuous variable, our analytic approach will be similar to the one described in Aim 1.

Handling Pregnancy: Because pregnancy events – particularly the third trimester – can have significant effects on glycemic control, we will ignore any HbA1c measures that occur during a pregnancy period, defined as 9 months before and 3 months after any code indicating a full-term delivery, pre-term delivery, miscarriage, or abortion procedure. We will also ignore any HbA1c measurements that occur during an inpatient hospitalization or during a treatment episode for oral steroid medications. We will also ignore diabetes medication use 9 months before and 3 months after any code indicating a full-term delivery, pre-term delivery, miscarriage, or abortion procedure.

Given the nature of the date ranges for the CDM data, we will not likely be able to construct a meaningful measure of Diabetes Duration at the time of surgery.

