**Table 5. PCORnet Bariatric Study Outcomes**

Aim 1	Aim 2	Aim 3

Primary Outcome: Percentage change in kg in adults (BMI z-score change in adolescents) at 1, 3, and 5 years
 
Secondary Outcomes:
 
 
1) weight regain* at 3 and 5 years; estimated as percent regain from the maximum weight (in kg) loss in the first 2 years;
 
2) a post-operative body weight that is <5% lower than the pre-surgical weight at 1, 3, 5 years after bariatric surgery; and
 
3) proportion achieving >5%, >10%, >20%, and >30% weight loss at 1, 3, and 5 years
 
	
Primary Outcomes: 1) Rate of diabetes remission (HbA1c <6.5% off diabetes medications);
 
Secondary Outcomes:
 
 
1) Rate of diabetes relapse after initial remission (restart of medication or HbA1c ≥6.5%)
 
2) Change in HbA1c at 1, 3, and 5 years
 
	
1. Primary Outcomes: 1) reoperation/ re-intervention is defined as any additional bariatric procedure and other procedures related to device removals, gastric revisions, abdominal or incisional hernia repair, laparoscopy or laparotomy, and percutaneous endoscopic gastronomy tube placements. We will look at endoscopy as a sensitivity analysis. Follow-up time is defined as the number of days after surgery until the first reoperation or re-intervention procedure code (if observed) or censoring.
 
Secondary Outcomes:
 
 
1. All-cause mortality is defined as any death during the study period. We will also examine the cause of death. Follow-up time is defined as the number of days after surgery until death (if observed) or censoring.
 
2. 30-day composite adverse event is defined using the LABS study and includes death; venous thromboembolism; percutaneous, endoscopic, or operative subsequent intervention; and, failure to be discharged from the hospitalization where the bariatric surgery was performed (within 30-days of surgery).
 

[figure not shown]
		
3. Rehospitalization is defined as any inpatient hospitalization following surgery that is not associated with a delivery, miscarriage, or abortion procedure code (using our previously defined list). Follow-up time is defined as the number of days after surgery until rehospitalization (if observed) or censoring.

--	--	---

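### Aim 2 relapse is compared only among patients who first remit, and a baseline propensity score for the full diabetes cohort does not balance that group, so the relapse hazard ratio can be biased

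*SAP*

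**What the plan says.** - **Outcome.** The Aim 2 synopsis lists "Rate of relapse of diabetes after initial remission" as a secondary outcome and applies the three pairwise comparisons to primary and secondary outcomes alike. Table 5 repeats it as "Rate of diabetes relapse after initial remission". The event is a restart of medication or an HbA1c of 6.5% or more.
- **Model.** The Aim 2 primary analysis section says "We will estimate the PSs as described in Aim 1, and fit a Cox proportional hazards model", but that sentence concerns remission. It then allows a stratified form: "we can fit a stratified Cox regression stratifying on site and site-specific PS percentiles (e.g., deciles". On secondary outcomes it says only "The secondary outcome of interest is the differential impact of the procedures on glycemic control, measured as change in HbA1c". Relapse gets no model, risk set or time origin there.
- **Propensity score.** Under Aim 1 the score is the "probability of receiving the treatment of interest (which can be chosen arbitrarily) in each pairwise comparison", given baseline confounders and calendar year, fitted at each site. The outcome model adds site. The Aim 3 primary analysis section describes Aims 1 and 2 as adjusting for propensity score decile, and the confounder section names propensity scores as the means of control. A re-fit among remitters is not mentioned.
- **Severity.** Table 6 rates baseline HbA1c and preoperative insulin use as strong predictors of both remission and relapse. The Aim 2 section expects that diabetes duration at surgery cannot be measured meaningfully.
- **Aims 4-6.** These list "Rate of relapse after initial remission (hazards ratio") as an outcome, but drop propensity scores in favour of a single covariate-adjusted regression.

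**The concern.** Remission happens after surgery and is itself the primary outcome on which the procedures are compared. Restricting to remitters therefore conditions on something the procedure can change. Suppose severe diabetes remits less often and relapses more often. A procedure that achieves fewer remissions may then achieve them mainly in milder patients, and those patients relapse less whatever procedure they had. Adjusting for the probability of receiving each procedure in the full cohort does not undo this, because the imbalance arises after assignment.

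At stake is how durability is read. A procedure that puts only the easier cases into remission could appear to give longer-lasting remission.

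**Working it through.** **Figures in the plan.** The SAP states no remission rate, relapse rate, event count or hazard ratio, so there is nothing to reproduce. Every rate and coefficient below is an assumption.

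**Step 1: when does balance survive?** At a fixed propensity score, let the share of mild patients be π under both procedures. Let p_m and p_s be the remission probabilities of mild and severe patients under a given procedure. Among remitters:

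mild share = π·p_m / (π·p_m + (1−π)·p_s) = 1 / (1 + ((1−π)/π)·(p_s/p_m))

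The two procedures stay balanced only if p_s/p_m is the same for both. With a common severity effect on the log-odds of remission, p_s/p_m is smaller where remission is less frequent, so that procedure's remitters are milder.

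**Step 2: hand example.** Take π = 0.5 and severity coded −1 (mild) or +1 (severe). The log-odds of remission falls by 1 per unit and the log relapse hazard rises by 0.5 per unit, so the severe-to-mild hazard ratio is e^1 = 2.718. Procedure has no effect on relapse.

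- Stronger procedure, 60% remission: p_m = 0.8195, p_s = 0.3805. Mild share 0.8195/1.2000 = 0.683. Mean starting hazard 0.683 + 0.317 × 2.718 = 1.545.
- Weaker procedure, 30% remission: p_m = 0.4864, p_s = 0.1136. Mild share 0.4864/0.6000 = 0.811. Mean starting hazard 0.811 + 0.189 × 2.718 = 1.325.
- Ratio, weaker to stronger: 1.325/1.545 = 0.86, where the truth is 1.00.
- With 60% against 55% (p_m = 0.7781, p_s = 0.3219 for the weaker), the ratio is 1.503/1.545 = 0.97. With equal remission it is 1.00.

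**Step 3: simulation, severity fully measured.** 12,000 patients, 4 replicates. Logit of assignment = Z + 0.2 × severity. Remission hazard 0.6 per year, multiplied by 0.3 for the weaker procedure. Relapse hazard 0.1 per year, follow-up to 5 years, true relapse HR 1.00. Cox model in remitters, stratified by decile of the full-cohort score.

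| Severity coefficient: remission / relapse | Remission, weaker vs stronger | HR, score deciles | HR, severity added |
|---|---|---|---|
| −0.5 / 0.5 | 59% vs 92% | 0.925 | 0.990 |
| −0.5 / 0.8 | 59% vs 92% | 0.894 | 0.990 |
| −1 / 0.5 | 57% vs 87% | 0.885 | 0.988 |
| −1 / 0.8 | 57% vs 87% | 0.834 | 0.986 |
| −0.5 / 0.5, remission multiplier 0.8 | 87% vs 92% | 0.987 | 0.997 |

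The standard error of log HR is 0.046 to 0.048 in the first four rows. The bias there runs from 0.078/0.046 = 1.7 to 0.182/0.048 = 3.8 standard errors. With 2,000 patients the standard error is 0.115, and the same biases are 0.7 and 1.6 standard errors.

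**Step 4: simulation with an unmeasured severity factor.** 12 replicates of 12,000 patients, two measured covariates and, where stated, one unmeasured factor. Logistic remission, baseline relapse hazard 0.10 per year, follow-up 1 to 5 years. HR is weaker vs stronger among remitters; the true HR is 1.00 unless stated.

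| Remission, stronger/weaker | Full-cohort score | Score re-fit in remitters | Measured covariates | All factors |
|---|---|---|---|---|
| 60/60 | 0.997 | 0.998 | 1.006 | 1.011 |
| 60/30, measured severity only | 0.919 | 1.007 | 1.018 | 1.018 |
| 60/30, plus unmeasured | 0.814 | 0.871 | 0.877 | 1.005 |
| 60/30, weak severity effects | 0.963 | 0.985 | 0.990 | 1.010 |
| 60/55, plus unmeasured | 0.962 | 0.972 | 0.980 | 1.008 |
| 85/40, strong effects | 0.604 | 0.697 | 0.702 | 1.001 |
| 60/30, true HR 1.5 | 1.208 | 1.295 | 1.306 | 1.517 |
| 60/30, unmeasured factor acts on remission only under the stronger procedure | 1.174 | 1.188 | 1.196 | 1.017 |

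Monte Carlo standard errors on log HR are 0.016 to 0.027, so the values near 0.96 are only about two standard errors from no bias.

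**The case against.** - **The premise is partly inferred.** No sentence says that relapse is adjusted with the full-cohort score; the Cox sentence is about remission. This stands as a limit on how the defect may be described. It does not remove the point: the propensity score is the control the plan describes for Aim 2, deciles are named in the Aim 3 section, and nothing else is offered for relapse.
- **The hazard ratio label belongs to Aims 4-6.** A reader might carry the propensity score argument over to those aims. The SAP does not support that, because they replace the score with covariate regression. Only unmeasured severity remains a concern there (0.877 in the 60/30 scenario).
- **Direction and size.** A reader might conclude that the weaker procedure's relapse hazard is certainly understated, and by a known amount. The documents give no remission rates and do not say which procedure remits less. The bias vanishes when remission rates are equal and reverses in the last scenario above. It also depends on assignment: when severity was the main driver of procedure choice (coefficient 1, with 0.2 for the other covariate), the decile-adjusted HR was 0.97 and 0.99. With both coefficients at 1 it was 0.94 and 0.91.
- **The plan reports that propensity adjustment did not change Aim 1-2 results.** Those statements give no figures and do not mention relapse. They also do not test the present question, which is whether remitters are balanced on severity.
- **Conditioning is already visible, and HbA1c change does not condition on remission.** Both are true, and they limit the harm. Neither corrects a between-procedure hazard ratio for relapse.

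**Conclusion.** The point holds for Aim 2 as a likely but uncertain bias in one secondary outcome. The primary remission comparison is not touched. The plan itself states that baseline HbA1c and insulin use drive both remission and relapse, and it provides no control suited to the group in which relapse can occur.

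The probable direction favours the procedure with less remission. This assumes that severe patients remit less and relapse more under every procedure, with a severity effect of similar strength. The size is illustrative: with measured severity only and large assumed remission differences, about 0.83 to 0.93 in place of 1.00; close to 1.00 when remission rates are similar; further from 1.00 when unmeasured severity also acts. A hazard ratio among remitters is still usable as a description of that group. It should not be read as the causal effect of procedure on relapse.

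**What to change.** For Aim 2 relapse, state in the SAP:

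1. The analysis set is patients who have remitted, with time starting at remission.
2. Baseline HbA1c, insulin use and number of oral medications (all in Table 6) enter the relapse Cox model directly, or the propensity score is re-estimated among remitters.
3. Baseline severity of remitters is tabulated by procedure.
4. The hazard ratio is reported as conditional on remission and not as a causal procedure effect, with a statement that selection on unmeasured severity, such as diabetes duration, remains.

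A full-cohort companion measure, such as the probability of being in remission at 1, 3 and 5 years, would be a useful addition because it does not condition on remitting.

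The cost is a few more model terms, one table and a re-run of one secondary analysis, with no new data. The SAP speaks of Aim 1-2 results in the past tense, so this may be a re-analysis and not only a change of wording. The repair removes only the measured part of the selection: in the 60/30 scenario with an unmeasured factor, the HR moved from 0.814 to 0.871 (score re-fit) or 0.877 (covariates), not to 1.00.
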